Phone Screen. Interested youth will call into our program line, and will be evaluated by our trained research assistant (RA) over the phone using our established phone screen. Youth referred by other research or community groups (such as the justice departments) will be contacted by an RA to receive more information about participation opportunities and to complete the phone screen if interested. During screening, potential participants will be informed of the general procedures for the study, and if interested, will answer several questions to establish potential eligibility.

For inclusion, youth must : **(1)** be aged 14-19, and complete the entire study before turning 21 **(2)** have not participated in any of the PI's prior or current studies, **(3)** be currently binge drinking (defined as 3+ drinks per drinking occasion for girls, and 4+ drinks per drinking occasion for boys; with a minimum of 1 binge drinking event during the past two months, with enrollment priority going to those who are heavier drinkers, e.g., ≥ 3 binge drinking events in the past month) ([name] et al 2013a), **(4)** have breath alcohol level of 0 before participating in all study components, **(5)** have not used recreational drugs, including prescription medications used without a prescription and/or used in a way counter to the intended dose/use, more than 3 times (total; doesn't have to be more than three uses of a single substance) in the past month (exceptions are marijuana, tobacco, and e-cigarette products, which are permitted due to high comorbidity with alcohol use) **(6)** agree to be contacted to participate for 3-, 6-, and 12-month follow-ups, **(7)** for youth ages ≤ 17 years: informed consent of a parent or legal guardian; and **(8)** all youth: personal informed assent/consent.

With respect to the fMRI component, we have attempted to maintain tight control over factors that may increase error variability and that maximize protection for our participants. Thus, our exclusion criteria are: (1) history of brain injury or neurological diagnoses (including loss of consciousness \geq 2 minutes), (2) currently taking psychotropic medications (e.g., neuroleptics, anticonvulsants), (3) current psychotic disorder, (4) neurodevelopmental disorder, (5) pregnancy (as self-reported or tested immediately prior to scans), (6) fMRI contra-indications (e.g., non-removable metal implants, braces, claustrophobia), and (7) left-handedness.

c) Vulnerable Populations

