Once a young person (under age 18) expresses interest and signs the informed assent, the research staff will contact the parent/guardian by phone, explain all aspects of the study, read the consent form verbatim, obtain verbal consent over the phone, and answer any questions that the parent or guardian has. Following previously successful procedures to verify the parents' identity over the phone, we first ask if the "parent or guardian of (insert adolescent's name) is home." Once that person is brought to the phone or if that person identifies him/herself

as the parent/guardian, we ask them to please state their full name. If the name given is not the same as that given to us by the adolescent, we thank them for their time and do not proceed with the consent. These conversations will be tape-recorded, logged, and kept for proof of consent. A copy of the consent form signed by the child will then be mailed to the parent or guardian for their records. We place the highest priority on parents/guardians being completely informed about what their child is being asked to do, and on making sure that we are indeed getting consent from a parent or legal guardian. We have tried other methods of obtaining consent (e.g., mailing consent forms home) and have either not received any response, or more importantly, have received consents of questionable validity. Further, mailing of consent information does not allow parents/guardians to ask detailed questions that they may have about the research prior to consenting. In the 10 years that the PI and colleagues have conducted research with adolescents, we have found phone consent to be the most reliable way to assure that we obtain fully informed consent with parents/guardians. During these 10 years of using phone consent, we have never had an adverse event related to consent. In fact, we have found that these conversations allow us to open the lines of communication between research staff and parents/guardians.

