for any reason, the youth's participation will be terminated. If a parent chooses to have their adolescent stop participating for any reason, the youth's participation will be terminated.

Procedures for withdrawal, including partial withdrawal. If a youth withdraws from the research, we will continue to retain the data collected until that point, unless they specifically request removal of their data from the study. In this event, we will destroy all of their data. Subject identifying information and any video recordings will be destroyed following the final study participant's completion of his or her 12-month follow up; therefore, if a participant requests that his or her data be removed following the conclusion of the study, we may not be able to complete the request as the data will no longer be identifiable as coming from a particular research subject.

7) Data and Specimens

a) Sharing of Results with Subjects

Incidental findings from Imaging. The MRI scan is being done to answer research questions, not to examine individual brains for medical reasons. This MRI scan is not a substitute for a clinical scan (the type a doctor would order). The research scan may not show problems that may be picked up by a clinical MRI scan. If we find an abnormality that appears to require urgent follow-up after review by a neuroradiologist on the study team, we will contact the participant by phone to help answer questions, recommend that the participant contact their doctor to schedule a clinical scan, and assist in getting the right follow-up care for the individual. It is possible that the individual could be unnecessarily worried if a problem were suspected, but not actually found. Our research team is always available to answer any questions the individual may have about their scan.

Incidental findings from pregnancy testing. Parents or guardians of a child participating in this study may be told the results of the child's pregnancy test if the child is younger than 15. If the child is 15 or older the pregnancy test result will be released to the child. It will be up to her whether or not it is released to the parent or guardian. However, if the Principal Investigator believes that the child is not receiving adequate medical care for the pregnancy, she will refer the subject to a place where the participant can get the proper care.

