Incidental findings from the questionnaires (CTQ, DPS). In the case that a participant's responses to any questionnaires, or spontaneous disclosure during a study visit, suggest that a participant may be having current thoughts of seriously hurting or killing him- or herself, or reports current physical or sexual abuse as a minor, the RA will elicit additional information as appropriate and call the Principal Investigator. If present, one of the study counselors may address these responses with the participant directly, calling the PI for additional support if needed. The PI may then initiate a conversation with the participant about his or her responses. If the investigator believes that the participant is a harm to him- or herself, at-risk for abuse as a minor, or that an abuser may be actively harming other minors, then the PI may voluntarily disclose this information to the appropriate parties (parent/guardian, Child Protective Services). In all cases, the RA will provide the participant with an updated resource sheet specific to the Portland area. To minimize "false alarms" and prevent unnecessary follow up, 4 short questions have been built into the computer questionnaires to filter out previously reported, historical incidents of possible child abuse. These questions immediately follow the Childhood Trauma Questionnaire so as not to appear abrupt or out of place in regard to subject matter.

b) Data and Specimen Banking

How and where data will be stored and the final disposition of the data/specimens.

Standard institutional practices will be followed as described in the OHSU information security and resource data guide (http://ozone.ohsu.edu/cc/sec/isq/res_sec.pdf) to maintain the

confidentiality and security of data collected in this study. Study staff will be trained with regard to these procedures.

Upon enrollment, subjects will be assigned a code that will be used instead of their name, medical record number or other personally identifying information. Electronic files for data analysis will only contain the subject code. Codes will not contain any part of the 18 HIPAA identifiers.

All data will be identified with a numeric code. Paper files will be stored in a locked cabinet separate from consent forms and confidential locator forms in restricted access offices at OHSU. Electronic data will be stored on encrypted computers and within restricted drives on the OHSU network. Access to all data/specimens will be restricted to study personnel.

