
Consistent with the PI's prior NIH funded work, all confidential locator forms will be destroyed upon participants' completion of the final follow-up.

Data released to other investigators will be labeled with only the code.

Follow up data from REDCap questionnaires will be stored upon collection in OCTRI's installation of REDCap, a highly secure and robust web-based research data collection and management system, then exported through REDCap to lab databases and stored as outlined above. Features of REDCap that protect participants' privacy and data security include:

- **Physical Security:** OCTRI's REDCap software is housed on servers located in ITG's Advanced Computing Center, providing locked physical security
- **Electronic Security:** The REDCap servers are housed behind both the OHSU firewall and a second ACC firewall. All web-based data transmissions are encrypted with industry-standard SSL methods.
- **Controlled User Access:** REDCap employs a robust multi-level security system that enables researchers to easily implement "minimum necessary" data access for their research staff, including specification of data fields that are identifiers. This feature includes "single click" ability to provide completely de-identified (removing all identified data fields and shifting dates) for analysis or other purposes. User activities are logged to enable auditing of all data access. Access is integrated with OHSU's network such that users who are also OHSU employees are authenticated against their OHSU network credentials.
- **Data Integrity:** REDCap is jointly managed in accordance with OHSU Information Security Directives by ACC staff and members of OCTRI's Biomedical Informatics Program, ensuring fidelity of database configuration and back-ups. User activities are logged to enable auditing of all data changes.

For future unspecified use. I intend to set up an approved repository to use de-identified data for future unspecified use (MRI scans; coded behavioral data, coded saliva samples). Please note: I will not be submitting anything into the repository until it is IRB approved. However, I would like to consent subjects now for those future uses. This will facilitate combining data from disparate subjects for the same subject, which may be needed.

8) Data Analysis

Power Analysis and Sample Size Requirements.

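### For an urgent MRI finding the protocol names only the participant as the person to be told, with no guardian step for participants aged 17 or under.

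*Combined protocol and SAP*

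**What the plan says.** Section 7a, Sharing of Results with Subjects, has three rules on incidental findings.

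- **Imaging.** If an abnormality looks urgent after neuroradiologist review, "we will contact the participant by phone to help answer questions, recommend that the participant contact their doctor to schedule a clinical scan". The same sentence goes on to promise practical help: "and assist in getting the right follow-up care for the individual". No age is mentioned, and no parent or guardian.
- **Pregnancy test.** A parent or guardian may be told if the child is under 15. From 15 the result goes to the youth: "It will be up to her whether or not it is released to the parent or guardian".
- **Questionnaires and disclosures.** If the PI sees a danger of self-harm or abuse, "then the PI may voluntarily disclose this information to the appropriate parties (parent/guardian, Child Protective Services"). The abuse triggers are that the youth is "at-risk for abuse as a minor, or that an abuser may be actively harming other minors".

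The inclusion criteria (section 5b) admit ages 14 to 19 and require, at 17 or under, "informed consent of a parent or legal guardian". Section 6 schedules two MRI scans, at Session 2 and at the 3-month follow-up.

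**The concern.** An abnormality judged urgent is time-sensitive. The imaging rule states who receives the call and the advice to see a doctor, and in both cases it is the participant. For a participant aged 14 to 17, whether the adult who consented to the study learns of the finding then depends on the youth passing it on or on staff practice that is not written down. Follow-up could be delayed. The matter is one of participant safety and has no bearing on the statistical inference.

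**Working it through.** No arithmetic bears on the conclusion, and the plan gives no figure to reproduce. The check is a reading of the relevant sections side by side.

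1. **Does the rule reach minors?** Yes. Eligible entry ages are 14, 15, 16, 17, 18 and 19, which is 6 single-year ages. Guardian consent is needed at 14, 15, 16 and 17, which is 4 of the 6. These are counts of ages, not of participants. With two scans planned per participant, a finding can arise on two occasions.

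2. **Does the imaging rule provide for a parent?** No. The call, the recommendation and the offer of help all refer to the participant or the individual. Nothing forbids telling a parent, and helping with care may well involve one, but no such step is stated.

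3. **Does another section supply the step?** No. The sections on minors (5c), consent (5f), scanning and follow-up (6), privacy (9) and risks (10a) contain no guardian contact for an urgent scan result. Section 10a leans the other way: it lists parents' wish to see adolescents' data as a risk to be minimised by protecting confidentiality. Staff who apply that section together with the imaging rule could reasonably decide not to call the guardian.

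4. **Do the neighbouring rules require parental contact?** No. The pregnancy rule leaves the decision to the youth at 15, 16 and 17, which is 3 of the 4 guardian-consent ages. The questionnaire rule leaves disclosure to the PI's discretion. Both at least tell staff how to handle the question of a parent; the imaging rule does not. A guardian step for imaging would therefore be a new safeguard, not alignment with an existing one.

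5. **Could staff reach the guardian?** Probably. In the default telephone consent procedure (section 5f), "the research staff will contact the parent/guardian by phone, explain all aspects of the study". Section 7b adds that "all confidential locator forms will be destroyed upon participants' completion of the final follow-up", so the forms are held through both scans, although their contents are not described. Missing contact details are not part of this concern.

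6. **How many minors would be affected?** This cannot be computed. The documents give neither the age distribution of enrolled youth nor a rate of urgent findings.

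**The case against.** The strongest objection is that the consent and assent forms are not in the supplied text, and they are where a guardian would naturally be told what happens with scan findings. By default the form is read to the guardian word for word, so the step may already exist there. This stands as a limit: the conclusion covers the protocol's rule and not the whole study file. If the form names a parent, the protocol should say the same, because staff will follow the protocol.

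Second, the rule does not say that only the participant may be told, and it obliges staff to help with care, so a minor is not left to act alone. That is correct, and it makes the risk smaller. It still does not ensure that the consenting adult is told.

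Third, the protocol often leaves disclosure to the youth or the PI, even for suicidal thoughts. Default parental contact for a possible scan abnormality, when the other is discretionary, is an uneven ordering. It could also spread to parents the needless worry that the imaging rule itself mentions. Both observations are fair. The PI exception and the restriction to findings already judged urgent reduce the difficulty without removing it.

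Finally, the frequency is unknown and the delay is not demonstrated. Both are true, and they argue for a small remedy rather than none.

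**Conclusion.** The concern holds. As written, the imaging rule can leave a participant as young as 14 as the only person told of an urgent brain abnormality, and no other part of the supplied text ensures that a guardian is informed. The change should be made: few cases are likely, but the harm from delay could be serious and the remedy is cheap. There is no effect on sample size, power, error rates or analysis. Confidence is medium, because the conclusion rests on two assumptions: that the unseen consent form does not already provide the step, and that staff would follow the rule as worded.

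**What to change.** Add one sentence to the imaging paragraph of section 7a, along these lines:

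> If the participant is 17 or under when the finding is made, staff will also contact the consenting parent or guardian, along with the youth, using contact details already held, unless the PI judges that this could put the youth at risk (for example, suspected abuse at home).

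- Limit the call to the scan finding. Alcohol use and other self-reported data stay out of it.
- Keep participant-only contact from age 18, in line with the re-consent at 18 in section 5f.
- Keep the existing commitment to help with follow-up care. The clinical recommendation remains with the investigator and the neuroradiologist.
- If the consent form already names a parent for imaging findings, carry its wording into section 7a instead.

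The cost is an extra call in rare cases, some worry for parents when a suspected problem proves unfounded, and slightly less privacy for the minor about the scan result. Section 10a already lists breach of confidentiality of neuroimaging data as a risk. Restricting the call to the scan finding answers the separate concern there about parents seeking adolescents' behavioural data.

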Phone Screen. Interested individuals will call into our program line, and will be evaluated by our trained research assistant (RA) over the phone using our established phone screen. Youth referred by other research or community groups will be contacted by an RA to receive more information about participation opportunities and to complete the phone screen if interested. During screening, potential participants will be informed of the general procedures for the study, and will answer several questions regarding alcohol and other substance use (e.g., how often do you use alcohol?), contra-indications for participating in an MRI study (e.g., do you have any medical implants?, have you ever welded?), and head injury history (e.g., have you ever lost consciousness?). Individuals will be informed that university researchers are developing

intervention programs, and thus a number of individual difference measures including brain imaging and genetic samples in the form of saliva will be collected. Individuals are told that this program discusses sensitive topics such as alcohol use and other risky health behaviors. All procedures will be carefully explained to potential participants. Eligible participants are invited in for the first available appointment.

Participant Incentives. Consistent with our prior NIH-approved work with youth, we will compensate youth in cash for their participation for in-person visits, and with gift cards for phone/REDCap visits (so that study staff do not need to mail cash). Youth will receive \$30 for Session 1, \$35 for Session 2, \$40 for the 3-month, \$45 for 6-month, and \$55 for the 12-month follow-up. The participant or their parent will be provided an additional \$15 for each of the first three sessions to offset transportation costs for a possible total of \$250. Youth who do not complete the study will receive compensation for the sessions they completed, and will receive full session compensation for any partially completed session (for example, if participant was unable to complete a scan for some reason, the participant would still receive full payment for that scan visit).

f) Consent Process

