Neuroimaging Session. We conduct the neuroimaging session during the second visit in order to have sufficient time to cater the counselor statements to the participant's in-session change talk statements, and to integrate their thematic content into each youth's individualized fMRI Neural In-Session Language Examination (NILE) task. Session 2 takes place at OHSU's Advanced Imaging Research Center (AIRC). Consistent with the PI's prior work ([name] under review), participants will be required to abstain from alcohol 24 hours prior to the scan as verified before the scan by breathalyzer, and will also complete a urinalysis to corroborate self-report as a measure of drug use and a voluntary test for pregnancy in females. Upon arrival to OHSU, youth will be screened to assure the absence of fMRI contraindications (no metal in body; not pregnant; breath alcohol = 0). Only approved youth will be scanned. We will use the 3T Siemens Prisma that includes 32 RF channels \times 102 coil elements, multi-nuclear support, clinical features (extremity coil, shoulder array coil, spectrus injector), and additional software (e.g., BLADE). fMRI scans will be collected with single-shot full k-space echo-planar imaging (EPI) with ramp sampling correction using the intercommissural line (AC-PC) as a reference (TR: 2.0s, TE: 27ms, α : 70°, matrix size: 64 \times 64, field of view: 24x24, 33 slices, voxel size: 3.75 \times 3.75 \times 4.5 mm). Image-based higher order automatic shimming will be employed. fMRI data will be acquired with the 32-channel phased array-coil. Automated analysis of scanner instability with the Weiskoff method will be carried out using a software tool provided by the MGH. A tilting acquisition will be used to improve the signal dropout and warping in the orbitofrontal cortex (Deichmann et al 2003) similar to our previous published studies ([name] et al 2013b). The subjects will complete a high-resolution structural scan collected for image registration and normalization, followed by the experimental procedure. The

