Sample size was selected to evaluate the primary research questions at a two-tailed alpha of .05 and power of .80. Estimates of effect size were conducted in G*Power 3 (Faul et al 2009, Faul et al 2007). For **Hypothesis 1**, the relationship between MI-consistent therapist statements and brain-based response, in our pilot evaluation, we found that MI-consistent behaviors (as contrasted with non-MI-consistent behaviors) showed a large effect size ($z = 2.27$, $d = 1.31$) within the IFG ([name] et al under review-a). Thus, this effect size requires a sample size of 22 subjects to power Hypothesis 1. In terms of **Hypothesis 2**, that brain activity will correlate with reductions in proximal and distal problem drinking, our pilot study showed significant relationships between MI-consistent therapist behaviors and proximal (1-month) reductions in binge drinking days (right IFG $z = 3.38$, $d = 1.95$; insula $z = 2.238$, $d = 1.29$) ([name] et al under review-a); thus, for this analysis, we would need 22 subjects to detect proximal behavior change. However, because no study to our knowledge has evaluated how BOLD response relates to youths' distal (12-month) behavior change, we suggest a more conservative (medium) effect size of $d = .70$ for this heretofore unexamined relationship. Together, this suggests the need for 68 youth to detect both proximal and distal behavior change for Hypothesis 2. For **Hypothesis 3** we refer to the work of Fritz and MacKinnon (2007) to determine sample size for our mediation hypothesis. For the A path, the relationship between therapist speech and adolescent BOLD response, our pilot evaluation suggests a large effect for MI-consistent therapist behaviors on BOLD activation. For the B path, the relationship between youth brain response and subsequent behavior change (proximal and distal treatment outcomes), we anticipate a medium effect size. For the indirect effect, that is, the effect of therapist speech upon problem drinking outcomes mediated by youth brain response, Fritz and MacKinnon indicate that with a large effect for the A path and a medium effect for the B path, we would need a sample of $N = 204$ to detect a mediated effect for Hypothesis 3 with power of .80 at an *a priori* alpha of .05.

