The Impact of Attrition. In our prior NIAAA R01 with drinking youth (PI [name]), we have an established track-record of retaining ~84% of adolescents at our most distal (12 month) follow-up. Thus, we project losing 16% of the proposed sample, thus requiring **N = 243** youth to account for attrition.

Analysis Plan.

Analyses will be conducted to evaluate (1) the relationship between therapist behavior and youth brain response (BOLD), (2) the relationship of youth brain response (BOLD) to changes in youth problem drinking across proximal (3- and 6-month) and distal (12-month) follow-ups, and (3) the mediational role of BOLD activation on the relationship between therapist behaviors and youth problem drinking outcomes. Measures will be derived from the baseline fMRI scan and behavioral data collected at baseline, 3-, 6- and 12-months.

fMRI preprocessing and single-subject analysis. The first three volumes of each run will be discarded to allow the MR signal to reach steady state. The remaining images in each youth's time series will be motion corrected (Jenkinson, Bannister, Brady, & Smith, 2002) using FSL's MCFLIRT module (FMRIB's Software Library). Images will be spatially smoothed with a 3D Gaussian kernel ($FWHM = 8 \text{ mm}^3$), intensity normalized and temporally filtered with a 50 sec high pass filter FEAT (FMRIB's Easy Analysis Tool) (Smith et al., 2004).

We will utilize a regression approach (GLM - general linear model) to extract regularities with regard to temporal aspects (i.e., time series) of the data. Statistical analysis will be carried out using FILM (FMRIB's Improved Linear Model) with local autocorrelation correction. We will create an explanatory variable (EV) for each trial type (MI-consistent, BAM-consistent, BAM- and MI-inconsistent). For each participant, we will use FILM to obtain a parameter estimate for each EV and create appropriate contrasts. Contrast maps of parameter estimates (PE) for each youth are transformed into a common stereotaxic space using the following 2-step registration prior to the group analyses. Statistical maps will be warped into the common MNI stereotaxic space (Jenkinson et al., 2002) before a random effect group analysis is performed. To do so, (1) the EPI image will be registered to the participant's high resolution T1 weighted image; (2) the T1-weighted high resolution image will be registered to the MNI 152 brain template image; and (3) statistical images

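### The 243 allows only for 12-month dropout; the 12-month mediation test also needs a usable Session 2 scan, and the documents give 243 two different meanings

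*Combined protocol and SAP*

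**What the plan says.** Section 8, Power Analysis and Sample Size Requirements, works "at a two-tailed alpha of .05 and power of .80". For Hypothesis 3 it takes a figure from a cited source for a design "with a large effect for the A path and a medium effect for the B path" and concludes that "we would need a sample of $N = 204$ to detect a mediated effect for Hypothesis 3 with power of .80". No numeric path values are given for this hypothesis.

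The next paragraph, The Impact of Attrition, rests on one fact from an earlier study: "we have an established track-record of retaining ~84% of adolescents at our most distal (12 month) follow-up". From this, "we project losing 16% of the proposed sample", "thus requiring N = 243 youth to account for attrition". No other loss is named.

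The Analysis Plan takes the brain measures from the baseline scan, which is the Session 2 scan. It builds both mediation paths from the BOLD contrast and the follow-up outcomes, and tests proximal and distal drinking separately.

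On scanning, section 6 (Neuroimaging Session) describes checks on arrival for metal, pregnancy and breath alcohol, and then says "Only approved youth will be scanned". Section 5e (Participant Incentives) provides for payment "if participant was unable to complete a scan for some reason". Section 9 lets a youth stop the scan at any time. Sections 5d and 6 (Follow-Up Procedures) allow the 6- and 12-month visits to be done by phone and online questionnaire.

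On the meaning of 243, section 2 gives it as the number to be enrolled. Section 5a gives it as the number who finish every study procedure, out of up to 500 screened or enrolled.

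**The concern.** A youth contributes to the 12-month test of Hypothesis 3 only with two things in hand: a usable BOLD contrast from Session 2 and a drinking outcome at 12 months. Section 8 describes no method for filling in a missing contrast. The attrition paragraph allows for loss of the second item only.

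The two losses need not fall on the same youth. No stated rule withdraws a youth who is turned away from the scanner or who stops a scan, and the 12-month outcome can be collected without a visit to the scanner site. Such a youth can be counted among the 84% retained and still be missing from the mediation analysis.

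What is at stake is whether the enrolment figure secures the number that the plan says it needs for its largest sample-size requirement. The two meanings of 243 make this harder to judge, because on one of them the losses have already been taken out.

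**Working it through.** **Inputs from the documents.** Required number for Hypothesis 3: 204 (section 8, Power Analysis). Retention at 12 months: about 84%, so loss 16% (section 8, Impact of Attrition). Planned number: 243 (same paragraph).

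**Input not in the documents.** Scan loss s, meaning a Session 2 scan that is missed, incomplete or unusable. No rate is given. I assume a range of 5% to 20% for illustration.

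**Step 1: the plan's own figure.** N = 204 / (1 - 0.16) = 204 / 0.84 = 242.86, rounded up to 243. The figure reproduces.

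**Step 2: the reserve left.** 243 x 0.84 = 204.12, so the margin over 204 is 0.12 of a youth. With 243 enrolled, the largest scan loss among retained youth that keeps the expected number at 204 is 1 - 204/204.12 = 0.0006, or about 0.06%. One such youth is enough to miss the target.

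**Step 3: evaluable number for the 12-month test, with 243 enrolled.** Two limiting cases:

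- independent losses: 243 x 0.84 x (1 - s)
- full overlap (as far as possible the same youth): 243 x min(0.84, 1 - s)

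| Assumed s | Independent | Short of 204 | Full overlap | Short of 204 |
|---|---|---|---|---|
| 5% | 193.9 | 10.1 | 204.1 | 0 |
| 10% | 183.7 | 20.3 | 204.1 | 0 |
| 15% | 173.5 | 30.5 | 204.1 | 0 |
| 20% | 163.3 | 40.7 | 194.4 | 9.6 |

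Under full overlap the number stays at 204 until s passes 16%.

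**Step 4: the other meaning of 243.** If 243 youth finish every procedure, as section 5a has it, up to 243 are evaluable and there is no shortfall. But then the step from 204 to 243 in section 8 has no purpose, since completers need no inflation for attrition. Section 5a also explains the 500 by the difficulty of reaching eligible youth, not by scan or follow-up loss.

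**Step 5: what a shortfall would do to power.** The 204 cannot be re-derived, because its source is not in the documents and the paths are described only in words. As a rough check I took d = 1.31 for the A path (the pilot value for Hypothesis 1) and d = 0.70 for the B path (the value assumed for distal change under Hypothesis 2). I converted each by r = d / sqrt(d^2 + 4), giving 0.55 and 0.33, and simulated the test that requires both paths to be significant, with no direct effect. Power was about 0.98 at 204, 0.97 at 184 and 0.95 at 163. This rests on pilot or assumed effects and does not validate the 204.

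**The case against.** The strongest reply has four parts.

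- **Overlap.** A youth who drops out between Sessions 1 and 2 would ordinarily have no 12-month outcome either, and so is already inside the 16%. This stands: such dropout must not be counted twice, and it is why the full-overlap case is shown. It does not cover a youth who fails a same-day check or stops a scan and then answers at 12 months by phone.
- **Thin evidence of scan loss.** Contraindications are asked at the phone screen and are exclusion criteria, the documents do not say whether a failed check can be rescheduled, and the payment clause is a hypothetical example that could equally concern the 3-month scan. No exclusion for motion or task performance is stated. This stands as to size: the rate may be small. It does not supply an allowance where none exists.
- **Section 5a.** If 243 are completers, nothing is missing. The text is there and must be dealt with, but it conflicts with section 2 and with the derivation in section 8, so it opens a second question and does not settle the first.
- **No shown harm.** On the rough check above, power stays well over 0.80 even at 163. This bears on how serious the point is, not on whether 243 secures the stated 204.

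A reader might go further and infer that the design is bound to deliver fewer than 204, that it will be 10 to 41 short, or that Hypothesis 3 is underpowered. The documents support none of these. The first needs some scan loss outside the 16% and needs 243 to mean enrolled. The second also needs an assumed rate and independence. The third is not borne out by the rough check.

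**Conclusion.** The point holds in a limited form. There is no arithmetic error in 243. As derived in section 8, however, it leaves no allowance for scan loss beyond the 16%, and any such loss among youth retained at 12 months takes the expected sample for the 12-month test of Hypothesis 3 below the stated requirement. The size cannot be fixed from the documents. With 243 enrolled and an assumed scan loss of 5% to 20%, the shortfall lies between zero (full overlap, up to 16%) and about 41 (independence, at 20%).

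The calculation concerns the 12-month test only. Retention at 3 and 6 months is not given, and those outcomes are tested separately. The missable 3-month scan does not matter here, because the analysis uses the baseline scan.

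Separately, and without any assumption, the documents use 243 both for youth enrolled before attrition (sections 2 and 8) and for youth finishing all procedures (section 5a). These cannot both be meant.

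**What to change.** 1. State whether 243 is the number enrolled or the number completing all procedures, and align sections 2, 5a and 8.
2. If it is the number enrolled, add to the attrition paragraph: of 243 enrolled, about 204 are expected to have a 12-month outcome; of these, a stated number are also expected to have a usable Session 2 scan. The scan-loss rate should be the sponsor's own, labelled as an assumption, with a word on whether the earlier 84% already counted youth lost around a scan. The 163 to 194 above are illustrations and should not be copied in as expected counts.
3. Give power for the 12-month test of Hypothesis 3 at that number, with the numeric path values used.
4. If 243 is the number of completers, restate the derivation from 204, because it would no longer be an attrition adjustment, and give the enrolment expected to produce 243.

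The cost is a few sentences and one power calculation. Enrolment need not change. If 243 is the number enrolled, the stated evaluable number may become somewhat less favourable.
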